### **7.2.2.2 Protocol Violation**

Any subject found to have entered this study in violation of the protocol will be discontinued from the study at the discretion of the Qualified Investigator. This will include any subject found to have been inappropriately enrolled (did not meet eligibility criteria). Subject non-compliance includes not showing up for study visits, not taking the investigational product as directed, or refusing to undergo study visit procedures. Subjects who are found to be taking prohibited medications or supplements without the knowledge of the Qualified Investigator will also be withdrawn. Any major protocol deviations (i.e., those that increase the risk to subjects and/or compromise the integrity of the study or its results) will result in subject discontinuation.

In case of an early withdrawal or discontinuation, no follow-up other than recovery of the investigational product and an attempt to perform laboratory safety tests, anthropometrics, and vitals will be done for the subjects who decide to end their participation, except if the withdrawal was due to medical reasons related to the study. In this case, subjects will be followed-up until recovery. If a subject withdraws or is removed from the study, information collected up until the point of withdrawal will be used unless the subject requests otherwise. The circumstances of any discontinuation will be documented in detail. A subject leaving the study prematurely will be replaced by another if study attrition exceeds the planned 20%. Subjects will be compensated for the part of the study that has been performed.

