### **8.3.4 Time Period and Frequency for Event Assessment and Follow-up**

The occurrence of an adverse event (AE) or serious adverse event (SAE) may come to the attention of study personnel during study visits and interviews of a study participant presenting for medical care, or upon review by a study monitor.

All AEs including local and systemic reactions not meeting the criteria for SAEs will be captured on the appropriate case report form (CRF). Information to be collected includes event description, time of onset,

clinician's assessment of severity, relationship to study product (assessed only by those with the training and authority to make a diagnosis), and time of resolution/stabilization of the event. All AEs occurring while on study must be documented appropriately regardless of relationship. All AEs will be followed to adequate resolution.

Any medical condition that is present at the time that the participant is screened will be considered as baseline and not reported as an AE. However, if the study participant's condition deteriorates at any time during the study, it will be recorded as an AE.

Changes in the severity of an AE will be documented to allow an assessment of the duration of the event at each level of severity to be performed. AEs characterized as intermittent require documentation of onset and duration of each episode.

The Qualified Investigator will record all reportable events with start dates occurring any time after informed consent is obtained until 7 (for non-serious AEs) or 30 days (for SAEs) after the last day of study participation. At each study visit, the investigator will inquire about the occurrence of AE/SAEs since the last visit. Events will be followed for outcome information until resolution or stabilization.

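### For participants who leave by choice, section 7.2.2.2 ends follow-up of an open AE that section 8.3.4 says must be followed to its outcome, and sections 8.3 and 8.3.4 end the AE window at different points

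*Combined protocol and SAP*

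**What the plan says.** Section 7.2.1 of the combined protocol and SAP lets a participant leave whenever and for whatever reason they choose. For early exits, section 7.2.2.2 provides that "no follow-up other than recovery of the investigational product and an attempt to perform laboratory safety tests, anthropometrics, and vitals will be done". The same sentence then states whom this limit covers and its one exception: it holds "for the subjects who decide to end their participation, except if the withdrawal was due to medical reasons related to the study". For the excepted group the section adds: "In this case, subjects will be followed-up until recovery". On data already held, it says that "information collected up until the point of withdrawal will be used unless the subject requests otherwise".

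Section 8.3.4 sets a general duty. On documentation: "All AEs occurring while on study must be documented appropriately regardless of relationship". On follow-up: "All AEs will be followed to adequate resolution", and again, "Events will be followed for outcome information until resolution or stabilization". It also has the investigator record reportable events that start "any time after informed consent is obtained until 7 (for non-serious AEs) or 30 days (for SAEs) after the last day of study participation". It contains no carve-out for people who withdraw.

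Section 8.3 gives a different end point: AE monitoring there runs only to the final visit.

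**The concern.** Someone who leaves for work or travel while a moderate AE is unresolved falls outside the exception in 7.2.2.2. Staff working from section 7 would make no further contact after the exit tests. Staff working from section 8 would follow the event to its outcome. Both texts are current, and nothing says which prevails.

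The stake is the participant's own follow-up and the completeness of the safety record. Causality is part of that record. Section 8.3.3.2 uses the response to stopping the product in its two highest categories, and it allows an event first rated possible to be upgraded when more information arrives. A leaver has usually just stopped the product, so ending contact at exit cuts off that information. The exception does not cure this, because it depends on a judgement about the reason for leaving that is made at the time of exit.

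**Working it through.** No sample-size or power figure is involved, so the check is a comparison of texts.

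**Which exits are in conflict?**

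| Situation | Under 7.2.2.2 | Under 8.3.4 | Conflict? |
|---|---|---|---|
| Stops the product only (7.1) | Not an exit; study procedures continue | AE followed | No |
| Leaves for a medical, study-related reason | Followed until recovery | Followed to resolution or stabilization | No, in substance |
| Withdrawn by the investigator for an SAE or an AE causing clinically significant illness (7.2.2.1) | Limit is worded for those who choose to leave | AE followed | No, on the wording |
| Leaves by choice for another reason, no AE open | No follow-up | Nothing open to follow | Only for new events after exit |
| Leaves by choice for another reason, AE open | No follow-up after the exit tests | AE followed to resolution or stabilization | **Yes** |

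**What is lost in the last row?**

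- *The count: nothing.* The AE began before exit. Section 8.3.4 requires it to be documented, and 7.2.2.2 keeps information gathered before withdrawal unless the participant asks otherwise.
- *The outcome: yes.* Resolution or stabilization after exit goes unrecorded if 7.2.2.2 is followed.
- *Causality: possibly.* A later upgrade under 8.3.3.2 would need information from after exit.

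**Does other text reconcile the two rules?** Sections 7.1, 7.2.1, 7.2.2, 7.2.2.1, 8.3 and 8.3.5 contain nothing that does. Section 7.2.2 asks for the end-of-study evaluations at withdrawal where possible, but that is a single assessment and cannot show how an open event ends.

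**End of the AE window.** Section 8.3 stops at the final visit. Section 8.3.4 runs to 7 days (non-serious) or 30 days (SAE) after the last day of participation. If that last day is taken as the day of exit or of the final visit (my assumption; the term is not defined), the end points differ by 7 or 30 days. The 7/30-day rule sorts events by onset date and schedules no contact. Section 8.3.4 notes that events may also surface when a participant seeks medical care. So a post-exit event can be recorded without a visit, but whether it is sought and counted depends on the section used. The mismatch also reaches completers, since neither section limits its window to leavers.

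**How many participants?** Sections 7.2.2 and 7.2.2.2 plan for 20% attrition:

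- on 2 × 62 = 124 (section 4.1): 0.20 × 124 = 24.8;
- on 130 (section 1.1): 0.20 × 130 = 26.

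These cover all reasons for leaving, and they are a planning figure, not a ceiling. The number affected is that total × (share leaving by choice outside the exception) × (share of those with an AE open). The documents give neither share, so no estimate follows.

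**Is conduct over?** If the enrolment dates in section 5.5 were kept, the last enrolment was by 31 March 2019. Adding 84 days of dosing gives 23 June 2019, and adding 30 days for SAEs gives 23 July 2019. Version 4.0 is dated 18 February 2022, 941 days later.

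**The case against.** The strongest reply is that the texts can be read together. Section 7.2.2.2 is a specific rule for people who choose to go, 8.3.4 is the general rule, and contact after withdrawal needs the participant's consent in any case. The leavers of most safety interest are already protected by the study-related medical exception, by 7.2.2.1 and by 7.1.

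Much of this stands, and it narrows the point. It does not remove it. No text gives the specific rule precedence. Section 8.3.4 says all AEs, regardless of relationship. And 7.2.2.2 ends follow-up even for leavers who would accept a call.

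A reader might infer more than the documents support:

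- *That open AEs drop out of the reported counts.* They do not; they are documented and used under both sections.
- *That SAEs are broadly lost.* Section 7.2.2.1 has any participant with an SAE withdrawn, and the limit is worded for those who decide to leave. An SAE open at a purely voluntary exit remains only as a narrow case.
- *That 7 or 30 days of active follow-up are cut to zero.* That window governs recording by onset date, so it is not comparable with follow-up.
- *That the different start points (consent in 8.3.4, enrolment in 8.3) matter.* The interval is at most 14 days (section 5.5) and precedes product use. Section 8.3 defines an AE in someone who has been given the product, so the difference has little content.
- *That efficacy or the comparison between arms is distorted.* The rule is the same in both arms, and section 9 sets out no safety analysis.

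**Conclusion.** The inconsistency is real and minor. For a participant who leaves by choice, outside the study-related medical exception and with an AE open, one section ends follow-up at exit and another requires it to continue until resolution or stabilization. The loss is the event's outcome and any later causality revision, mainly for non-serious AEs. The different window ends in 8.3 and 8.3.4 are a second, separate inconsistency, about whether events after exit are sought and counted.

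The conclusion rests on reading 7.2.2.2 as written, with its limit applying to those who decide to leave, and on finding no text that ranks the sections. The size in participants is unknown. Sample size, power and the efficacy results are unaffected.

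**What to change.** - In 7.2.2.2, add: any AE open at withdrawal is followed under section 8.3.4 regardless of relatedness, subject to the participant's agreement.
- In 8.3, change the end of the window to match 8.3.4: 7 days for non-serious AEs and 30 days for SAEs after the last day of participation.
- If conduct is finished, as the dates suggest, report AEs over that one window and state how many leavers had an AE whose outcome is unknown.

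The cost is two changes of wording and a few follow-up contacts. If conduct is finished there are no contacts, only one counting rule and one extra count in the report.

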## **8. Study Assessments and Procedures**

### **8.1 Efficacy Assessments**

The efficacy of Proglucamune® on PQi and GQi status will be quantified as outlined in the PQD scoring system (Table 1 & Table 2) and the GQ scoring system (Table 3 & Table 4). Each subject's PQi and GQi status – as reflected in their PQD and GQD score – for each visit will be used to determine whether or not the subject's PQi or GQi status is improved by Proglucamune®. Treatment efficacy will also be evaluated by measuring and comparing salivary IgA levels at day 1 (Study Visit 1), day 42 (Study Visit 4) and day 84 (Study Visit 7).

### **8.2 Safety and Other Assessments**

The active ingredients in treatment don't have safety information for pregnant. In order to protect participants, any participants who are pregnant or planning to become pregnant will be excluded. Since treatment product contains yeast, extract of mushroom, any participants, who are allergy to yeast, mushroom, and other fungi, will be excluded. The treatment in this study is a supplement, not a medicine. To avoid interrupting patients' treatment, participants will be evaluated whether he/she was extremely ill, immune deficient during the screening. Any participants who are extremely ill, immune deficient will be excluded too.

### **8.3 Adverse Events and Serious Adverse Events**

Participants will be monitored for adverse events from the time of enrollment through the final visit. An adverse event (AE) is any untoward medical occurrence in a participant in a clinical investigation who has been administered an investigational product and which does not necessarily have a causal relationship with this treatment. An AE can be any unfavorable and unintended sign (including an abnormal laboratory finding), symptom, or disease temporally associated with the use of a product, whether or not it is considered related to that product. Pre-existing conditions which worsen during a study are to be reported as AEs.

During the study, participants will be asked to make a note of any adverse events. At each visit the participant will be asked "Have you experienced any difficulties or problems since I saw you last"? Any AEs will be documented and in the study record and will be classified according to the description, duration, intensity, frequency, and outcome. The Qualified Investigator will assess any AEs and decide causality.

#### **8.3.1 Definition of Adverse Events (AE)**

Adverse event means any untoward medical occurrence associated with the use of an intervention in humans, whether or not considered intervention-related (21 CFR 312.32 (a)).

### **8.3.2 Definition of Serious Adverse Events (AE)**

A serious adverse event (SAE) is any experience that suggests a significant hazard, contraindication, side effect or precaution. It is any AE that results in any of the following outcomes:

- Death
- A life-threatening adverse event
- Inpatient hospitalization or prolongation of existing hospitalization
- A persistent or significant disability or incapacity
- A congenital anomaly/birth defect in the offspring of a participant who received the study treatment
- Important medical events that may not be immediately life-threatening or result in death or hospitalization but may jeopardize the participant or may require intervention to prevent one of the outcomes listed above. Examples of such events are intensive treatment in an emergency room or at home for allergic bronchospasm; blood dyscrasias or convulsions that do not result in hospitalization; or the development of drug dependency or drug abuse.

### **8.3.3 Classification of An Adverse Event**

#### **8.3.3.1 Severity of Event**

Intensity of AEs will be graded on a three-point scale (mild, moderate, severe) and reported in detail in the study record

1. Mild: Awareness of event but easily tolerated
2. Moderate: Discomfort enough to cause some interference with usual activity
3. Severe: Inability to carry out usual activity

#### **8.3.3.2 Relationship to Study Intervention**

The causality relationship of investigational product to the adverse event will be assessed by the Qualified Investigator as either:

1. Most probable: There is clear evidence to suggest a causal relationship, and other possible contributing factors can be ruled out. The clinical event, including an abnormal laboratory test result, occurs in a plausible time relationship to study intervention administration and cannot be explained by concurrent disease or other drugs or chemicals. The response to withdrawal of the study intervention (dechallenge)

should be clinically plausible. The event must be pharmacologically or phenomenologically definitive, with use of a satisfactory rechallenge procedure if necessary.

2. Probable: There is evidence to suggest a causal relationship, and the influence of other factors is unlikely. The clinical event, including an abnormal laboratory test result, occurs within a reasonable time after administration of the study intervention, is unlikely to be attributed to concurrent disease or other drugs or chemicals, and follows a clinically reasonable response on withdrawal (dechallenge). Rechallenge information is not required to fulfill this definition.
3. Possible: There is some evidence to suggest a causal relationship (e.g., the event occurred within a reasonable time after administration of the trial medication). However, other factors may have contributed to the event (e.g., the participant's clinical condition, other concomitant events). Although an AE may rate only as "possibly related" soon after discovery, it can be flagged as requiring more information and later be upgraded to "probably related" or "definitely related", as appropriate.
4. Unlikely: A clinical event, including an abnormal laboratory test result, whose temporal relationship to study intervention administration makes a causal relationship improbable (e.g., the event did not occur within a reasonable time after administration of the study intervention) and in which other drugs or chemicals or underlying disease provides plausible explanations (e.g., the participant's clinical condition, other concomitant treatments).
5. Not related: The AE is completely independent of study intervention administration, and/or evidence exists that the event is definitely related to another etiology. There must be an alternative, definitive etiology documented by the clinician.

### **8.3.3.3 Expectedness**

The Qualified Investigator will be responsible for determining whether an adverse event (AE) is expected or unexpected. An AE will be considered unexpected if the nature, severity, or frequency of the event is not consistent with the risk information previously described for the study intervention.

### **8.3.4 Time Period and Frequency for Event Assessment and Follow-up**

The occurrence of an adverse event (AE) or serious adverse event (SAE) may come to the attention of study personnel during study visits and interviews of a study participant presenting for medical care, or upon review by a study monitor.

All AEs including local and systemic reactions not meeting the criteria for SAEs will be captured on the appropriate case report form (CRF). Information to be collected includes event description, time of onset,

clinician's assessment of severity, relationship to study product (assessed only by those with the training and authority to make a diagnosis), and time of resolution/stabilization of the event. All AEs occurring while on study must be documented appropriately regardless of relationship. All AEs will be followed to adequate resolution.

Any medical condition that is present at the time that the participant is screened will be considered as baseline and not reported as an AE. However, if the study participant's condition deteriorates at any time during the study, it will be recorded as an AE.

Changes in the severity of an AE will be documented to allow an assessment of the duration of the event at each level of severity to be performed. AEs characterized as intermittent require documentation of onset and duration of each episode.

The Qualified Investigator will record all reportable events with start dates occurring any time after informed consent is obtained until 7 (for non-serious AEs) or 30 days (for SAEs) after the last day of study participation. At each study visit, the investigator will inquire about the occurrence of AE/SAEs since the last visit. Events will be followed for outcome information until resolution or stabilization.

### **8.3.5 Adverse Event Reporting**

During the study, participants will be asked to make a note of any adverse events. At each visit the participant will be asked "Have you experienced any difficulties or problems since I saw you last"? Any AEs will be documented in the study record.

The Qualified Investigator will be responsible for classification of an AE as an SAE within 24 hours of notification. Causality will be signed off by the Qualified Investigator prior to reporting to ethics and regulatory bodies. Notification of any serious adverse events will be made in writing to the study sponsor. The IRB will be notified of all SAEs and unexpected adverse reactions. All SAEs will be reported to the Therapeutics Products Directorate (TPD) in an expedited manner.

The sponsor must notify the TPD of all serious adverse reactions as follows:

1. If it is neither fatal or life threatening, within 15 calendar days after the day on which the sponsor becomes aware of the information; and
2. If it is fatal or life threatening, must be reported as soon as possible, but not later than seven (7) days after the day on which the sponsor becomes aware of the information.

### **8.3.6 Serious Adverse Event Reporting**

In accordance with Natural Health Products Directorate (NHPD) guidelines:

- If the serious unexpected adverse reaction is fatal or life threatening, the NHPD will be notified immediately if possible, and no later than seven days after the sponsor becomes aware of the information
- If the serious unexpected adverse reaction is neither fatal nor life threatening, the NHPD will be notified immediately if possible, and no later than 15 days after the sponsor becomes aware of the information
- Within eight days after having informed the NHPD of a serious unexpected adverse reaction to the NHP, the sponsor must submit a report as complete as possible that includes an assessment of the importance and implication of any findings. The final report should include relevant previous experience with the same or similar health products.
- Serious adverse events unrelated to the NHP being studied do not require expedited reporting to the NHPD.
- In situations in which the cause of the adverse event is uncertain, the report will be submitted in the expedited manner and the problem in ascribing a cause should be addressed in a cover letter.

## **8.4 Unanticipated Problems**

### **8.4.1 Definition of Unanticipated Problems (UP)**

The Office for Human Research Protections (OHRP) considers unanticipated problems involving risks to participants or others to include, in general, any incident, experience, or outcome that meets **all** of the following criteria:

- Unexpected in terms of nature, severity, or frequency given (a) the research procedures that are described in the protocol-related documents, such as the Institutional Review Board (IRB)-approved research protocol and informed consent document; and (b) the characteristics of the participant population being studied;
- Related or possibly related to participation in the research (“possibly related” means there is a reasonable possibility that the incident, experience, or outcome may have been caused by the procedures involved in the research); and
- Suggests that the research places participants or others at a greater risk of harm (including physical, psychological, economic, or social harm) than was previously known or recognized.

